#### Exclusion Criteria

- The subject has an HS-PGA score of 0 or 1
- The subject has received ILTAC less than 8 days prior to the initial visit.
- The subject does not have capacity to consent to the study.
- The subject has taken systemic steroids at least 4 weeks prior to the time of enrollment.
- The subject has a known allergy or history of adverse reaction to steroids.
- The subject is pregnant.
- Subjects who have received a biologic therapy two weeks before and during the study period.

d) Justification of exclusion of pregnant patients: ILTAC-40 is pregnancy category C.

e) Subjects who do not have the capacity to consent will not be enrolled in the study.

f) The sources of research material include the photographs and patient surveys, which will be obtained by individually identifiable living human subjects. The photographs are part of routine clinical care. The patient surveys will be for the specific purpose of research.

## 4.0 PARTICIPANT RECRUITMENT

- Those receiving care through the HSC at Montefiore Medical Center will be invited to enroll in the trial. It is estimated that the research team will have the capacity to screen and enroll 5 new patients per clinic. The day prior to each clinic, research personnel will use a random number generator to identify 8 potentially eligible patients based on inclusion/exclusion criteria, considering refusals or ineligibility, during the screening. After obtaining informed consent, patients will be enrolled in the study.
- We will register our study on <https://clinicaltrials.gov>.
- It will be explained that treatment will not be different for patients who do not wish to enroll in the study. Study participation is completely voluntary, and patients can choose to withdraw at any time.
- Patients privacy will be protected by assigning each participant a unique identifier for any analysis (see below for details).

## 5.0 INFORMED CONSENT

- Informed Consent containing all of the necessary elements is provided.
- The Informed Consent Process
  - The PI or clinician will obtain informed consent.
  - Prior to the initiation of any study related procedures, the potential subjects will be given a copy of the most recent IRB stamped and approved informed consent to read.
  - The PI or clinician will discuss the specifics of the study including but not limited to the purpose of the research, procedures, time commitment, required tasks, alternative

treatments, benefits, risks, confidentiality, etc. in a comprehensible (non-scientific) manner, using language readily understandable by the subject.

- The person consenting will assure the voluntariness of the subject. Subjects will be told that participation is voluntary and that, if they do not consent, they will not be penalized in any way.
- A private, confidential setting will be provided for the potential subject to read and discuss the informed consent free from coercion, undue influence or constraints of time. All subjects will be given a chance to ask questions and express concerns. They will be given the option to take the consent home and discuss it with family, friends, and/or health care providers.
- After a subject and the person conducting the consenting signs and dates the consent, the subject will be given a copy of the signed informed consent form.
- An enrollment note will be written in the EMR document as to who obtained consent, how, when, were questions asked and answered, and that a copy of the informed consent was given to the subject.

c) No waiver/alteration of the informed consent process is requested.

d) Informed consent will be obtained by the parent or legal guardian of all minors. In addition minors between the ages of 13 to 17 who are capable to give assent will sign the same Informed Consent Document as the parent or legal guardian.

e) The treatment is for research purposes and there will be no cost to the patient. The initial visit, the four week follow up, and the laboratory tests are standard clinical care and will be billed to the patient's insurance. No remuneration will be offered for participation. Montefiore HIPAA procedures and policies will be followed.

f) Study Calendar

|  | Enrollment | Day 2 | Day 6 | Week 2 | Week 4 |
|--|------------|-------|-------|--------|--------|
| Photograph   | X          |       |       | X      | X      |
| HS-PGA   | X          |       |       | X      | X      |
| Treatment: NS,
ILTAC-10,
ILTAC-20 or
ILTAC-40 | X          |       |       |        |        |
| Patient
Satisfaction
Survey                      | X          | X     | X     | X      | X      |
| PROMIS
Survey                                       | X          | X     | X     | X      | X      |
| NRS Pain Scale   | X          | X     | X     | X      | X      |
| Side Effect
Assessment                              |            | X     | X     | X      | X      |

## 6.0 RISK/BENEFIT

a) The protocol here is considered greater than minimal risk, due to injection of medication or placebo. The initial risk of injection is temporary discomfort during the treatment. Potential side effects of the treatment include thinning/atrophy of the skin, acneiform lesions, capillary dilations, dyschromia, and HPA axis suppression. A psychological risk

of disappointment may occur if participation does not lead to a clinical improvement. Breach of confidentiality is a possible risk if data is lost or stolen.

- b) Risk will be minimized as follows:  
Confidentiality will be maintained by keeping records in secure areas in the clinic. Patient-identifiable materials, such as paper administered surveys and consent forms will be kept in secure areas, i.e., lockable storage rooms. Computer files are accessible via password-protected computers that kept in lockable rooms. All lab personnel that work with patient data have passed human subject protection courses, and certification of this is on file in the IRB office. No patient identifiers will be included in the analytic datasets. All results will be presented and published as aggregate results without patient identifiers.
- c) In our experience to date, patients are pleased to be involved in the HSC and gratified to assist in further advancing our current knowledge of this poorly understood and immensely debilitating disease. Potential benefits for individual patients include improvement or resolution of HS symptoms. Additionally, patients will be receiving personalized care by a team of experts, as well as the psychological benefits of receiving care at a multidisciplinary treatment center. There will be additional benefit for the group of HS patients as we learn to optimize the treatment of acute flares.
- d) Data will be stored in a de-identified manner, using a CGP-coding scheme. The Safe Harbor method will be used to de-identify one PHI specific identifier (patient name) by creating a unique code for each patient. The list of patient names and codes will be kept in a separate and secure location, on an Idrive on Montefiore Computer system, with restricted access only to approved individuals. The data will be carefully entered and analyzed in statistical programs. The data will be checked and edited by members of the research team. No individuals other than members of the research team, will have access to the data. All lab personnel that work with patient data or samples have passed human subject protection courses, and certification of this is on file in the IRB office. All physical data will be maintained at a designated site, in a locked cabinet, in a locked room.

## 7.0 DATA ANALYSIS

- a) Statistical Methods  
We will analyze the data from the study using an intention to treat approach. Categorical variables, including presence of side effects, drainage, and physical function, will be analyzed with chi square tests. Continuous variables, such as NRS pain scale, markers of inflammation, and lesion size, will be analyzed by T-test. Sensitivity analyses or exploratory analyses may be performed to examine the effect difference for race or gender. In the unlikely case patients do not receive the treatment they will still be randomized for analysis using a per protocol approach. All statistical tests will be 2-sided, with  $p < 0.05$  considered significant.
- b) There will be no interim analysis or early stopping of the study.
- c) Confounding and effect modification will be addressed by randomization of the subjects and blinding of both the investigators and the participants.
- d) If subjects are lost to follow up, they will be analyzed in the group to which they were initially randomized.

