##### *Secondary Outcomes*

- Change from baseline in NRS pain scale at days 2, 6, and 14.
- Difference in change from baseline in NRS pain scale at days 2, 6, 14, and 28 between ILTAC-10, ILTAC-20, ILTAC-40.
- Change from baseline in HS-PGA score at week 2 and 4.
- Difference in change from baseline in HS-PGA score at week 2 and 4 between ILTAC-10, ILTAC-20, ILTAC-40.
- Change from baseline in objective markers of inflammation (c-reactive protein [CRP], erythrocyte sedimentation rate [ESR], and interleukin-6 [IL-6]) at week 2 and 4.

- Change from baseline in subjective markers of inflammation (erythema, edema, and suppuration) at week 2 and 4.
- Change from baseline in lesion size at week 2 and 4.
- Difference in change from baseline in lesion size at week 2 and 4 between ILTAC-10, ILTAC-20, ILTAC-40.
- Change from baseline in Patient-Reported Outcomes Measurement Information System (PROMIS) measure of physical functioning at days 2, 6, 14, and 28.
- Difference in change from baseline in PROMIS at days 2, 6, 14, and 28 between ILTAC-10, ILTAC-20, ILTAC-40.
- Proportion of subjects reporting side effects at days 2, 6, 14, and 28.
- Difference in proportion of subjects reporting side effects at days 2, 6, 14, and 28 between ILTAC-10, ILTAC-20, ILTAC-40.
- Baseline patient satisfaction.
- Change from baseline in patient satisfaction at days 2, 6, 14, and 28.
- Serum cortisol and ACTH levels at week 2 and 4.
- Change in serum cortisol and ACTH levels from week 2 to 4.

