Participant eligibility will be assessed according to inclusion and exclusion criteria in 2.0a. A member of the study team will describe the study and answer any of the participant's questions. The participant will then be consented and enrolled. The initial visit and all subsequent visits will include documentation of NRS pain scale (Appendix B), HS-PGA, Hurley Stage (Appendix C), clinical markers of inflammation, and lesion size (as specified in our standard approach to care. Photographs of the lesions will be obtained. The study personnel will administer a patient satisfaction survey and the PROMIS questionnaire, which will take 15 minutes to complete (Appendix D and Appendix F [or Appendix G if pediatric]). Chart review will record demographic information (age, gender, race, ethnicity, smoking status, and BMI) and complete blood count (CBC), basic metabolic profile (BMP), liver function tests (LFT), erythrocyte sedimentation rate (ESR), c-reactive protein (CRP), and interleukin-6 (IL-6). The lab work is a standard of care at the HSC independent of research objectives. The patient will receive an injection, not to exceed 2 mL per anatomic area, in up to 3 anatomic areas (total of 3mL). The patient will be counseled regarding potential side-effects of the treatment (Appendix H) and asked to monitor accordingly. No other changes to the patient's HS medication regimen will be made for the duration of the study.

- Phone Contact 1 (2-day post-treatment)

Since triamcinolone has a half-life of 18 to 36 hours, the initial patient follow-up will be a phone call at 2 days post-injection, lasting 15 minutes. Study personnel will administer a patient satisfaction survey and the PROMIS questionnaire (Appendix D, and Appendix F [or Appendix G if pediatric]). Additionally, patients will be asked if they experienced any side effects, including thinning/atrophy of skin, acneiform lesions, capillary dilation, and/or dyschromia.

- Phone Contact 2 (6 days post-injection)

This 15 minute phone call will be 6 days post-injection and will involve administering the patient satisfaction survey, the PROMIS questionnaire, and questions about side effects.

- Visit 2 (2 weeks post-injection)

- The initial screening visit examination will be repeated at week 2. Additionally, the patient will be asked to identify side effects. A patient

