#### c) Outcome Measures Pertaining to Each Aim

- *Aim 1:* To compare efficacy of ILTAC-10, ILTAC-20, and ILTAC-40 versus placebo, we will measure the change from baseline in pain, objective and subjective markers of inflammation, physical functioning, and lesion size as well as comparing these changes among the different treatment groups. Change from pain baseline will be quantified by comparison of the NRS pain scale across different treatment groups (Appendix B). Objective markers of inflammation include c-reactive protein (CRP), erythrocyte sedimentation rate (ESR), and interleukin-6 (IL-6), which will be obtained from chart review of standard of care initial, 2 week, and 4 week follow-up HS visit. Erythema and edema will be measured clinically based on a 5-point ordinal scale (Appendix E). Suppuration will be measured on a dichotomous scale, by the presence or absence of purulent drainage from the lesion. Physical functioning will be measured by change from baseline in the Patient-Reported Outcomes Measurement Information System (PROMIS) measure of physical functioning. Separate forms will be administered for adult and pediatric participants. A one point change, either positive (improvement) or negative (decline), will be considered clinically meaningful (Appendix F and Appendix G). Lesion size will be measured in centimeters at baseline and during the week 2 and 4 visit.

- *Aim 2:* Side effects of ILTAC-10, ILTAC-20, and ILTAC-40 that will be investigated include thinning/atrophy of the skin, acneiform lesions, capillary dilations, and dyschromia. Hypothalamic-pituitary-adrenal (HPA) axis suppression will be obtained through chart review of standard of care serum 8 AM cortisol and ACTH levels at week 2 and 4 follow-up HS visits. Self-evaluations will be conducted by the patient and documented via telephone interviews. Clinical-evaluations will be conducted at the follow-up visits.
- *Aim 3:* To measure the patient's satisfaction after treatment, we will compare the results from the satisfaction survey between the different treatment groups at baseline, day 2, day 6, week 2, and week 4. The patient satisfaction survey will address disease control, and response to injection (in terms of pain, drainage, and lesion size), and quality of life (Appendix D).

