## 8.0 DATA QUALITY CONTROL AND DATABASE MANAGEMENT

- a) Data will be stored in a de-identified manner, with a CGP-coding scheme. The Safe Harbor method will be used to de-identify one PHI specific identifier (patient name) by creating a unique code for each patient. The list of patient names and codes will be kept in a separate and secure location, on an Idrive on Montefiore Computer system, with restricted access only to approved individuals. The data will be carefully entered and analyzed in statistical programs such as excel. The data will be checked and edited by the members of the research team. No individuals other than members of the research team will have access to the data. All lab personnel that work with patient data or samples have passed human subject protection courses, and certification of this is on file in the IRB office. All physical data are kept in a designated site, in a locked cabinet in a lockable room.
- b) Subject treatment assignments will remain blinded until the final subject has completed follow up and all data has been recorded and validated. Urgent, immediate unblinding due to medical emergency may be authorized by the Investigator. All instances of subject unblinding will be documented in the study record.

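### Section 7.0(a) assigns physical function to chi-square tests, but the outcome is change in a multi-item PROMIS score, and the one-point rule has no unit and no stated link to the test

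*Combined protocol and SAP*

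**What the plan says.** Section 7.0(a) sorts outcomes into two lists. The first reads "Categorical variables, including presence of side effects, drainage, and physical function, will be analyzed with chi square tests". The second reads "Continuous variables, such as NRS pain scale, markers of inflammation, and lesion size, will be analyzed by T-test". PROMIS is not named in either list. Section 2.0(c), Aim 1, makes it the measure of physical function: "Physical functioning will be measured by change from baseline in the Patient-Reported Outcomes Measurement Information System (PROMIS) measure of physical functioning".

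The Secondary Outcomes list change in PROMIS at four follow-up times and, separately, "Difference in change from baseline in PROMIS at days 2, 6, 14, and 28 between ILTAC-10, ILTAC-20, ILTAC-40". Aim 1 in 2.0(c) also compares these changes across the treatment groups.

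On interpretation, 2.0(c) says "Separate forms will be administered for adult and pediatric participants", and then "A one point change, either positive (improvement) or negative (decline), will be considered clinically meaningful". That last sentence goes on to point to both Appendix F (adult) and Appendix G (pediatric) and cites reference 20, whose title concerns PROMIS-Cancer scales. The adult form has 10 items and asks about function now. The pediatric form has 8 mobility items and asks about the past 7 days. Every item on both is scored 1 to 5.

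**The concern.** A chi-square test needs categories, and the plan defines none for physical function. The outcome as written is a change in a score with many levels. The test as written compares proportions, so it does not estimate that change or the difference in it between arms. The plan uses a t-test for the 11-point pain scale but treats the finer PROMIS score as categorical, without giving a reason.

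The one-point rule is the only candidate for the categories. An analyst would have to infer that link and then choose the unit: raw sum, item average or standardised score. That choice decides who counts as improved. PROMIS is an Aim 1 efficacy measure at days 2, 6, 14 and 28, so the choice affects a whole family of secondary results. It could also be made after scores have been seen.

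**Working it through.** **The plan's own power figure.** The only power calculation is for pain (3.0(b), Table 1). Inputs: difference 1, SD 1 at each time, correlation 0.1, two-sided alpha 0.05, 30 per arm. SD of change = √(2 − 2 × 0.1) = 1.342. The noncentral t distribution gives power 0.810, as Table 1 states. The standardised effect is 1/1.342 = 0.745, used below as 0.74. No PROMIS effect, SD or distribution is given.

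**What one point could mean** (item counts and scores from Appendices F and G).
- Adult raw sum: 10 to 50, range 40, 41 levels. One raw point = 1/40 = 2.5% of the range.
- Pediatric raw sum: 8 to 40, range 32, 33 levels. One raw point = 1/32 = 3.1%.
- Item average: 1 to 5, range 4. One point = 1/4 = 25%, which is 10 raw points (adult) or 8 (pediatric).

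The same rule therefore differs 8- to 10-fold between the raw-sum and item-average readings.

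**Power, for illustration only.** Assume normally distributed change with equal SDs, 30 per arm and a true difference of d SDs. The two-category cut most favourable to chi-square lies midway between the arm means, so the proportions above it are 1 − Φ(d/2) and Φ(d/2). Chi-square power is exact for the uncorrected Pearson test.

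| d (assumed) | Proportions above best cut | t-test | Best-cut chi-square |
|---|---|---|---|
| 0.3 | 0.44 vs 0.56 | 21% | 16% |
| 0.5 | 0.40 vs 0.60 | 48% | 34% |
| 0.74 | 0.36 vs 0.64 | 80% | 63% |
| 1.0 | 0.31 vs 0.69 | 97% | 87% |

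At d = 0.74, the chi-square sample size for 80% power, by normal approximation, is [1.96√(2 × 0.5 × 0.5) + 0.842√(0.356 × 0.644 + 0.644 × 0.356)]² / (0.644 − 0.356)², or about 46 per arm.

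**Cut at one raw point.** Take d = 0.74, change rounded to whole points, and an assumed SD of change of 3, 5 or 8 raw points.
- Improved versus not: 61%, 60% and 60% if controls do not change on average; 57%, 57% and 58% if controls gain one point.
- Three categories, by simulation: 54%, 52% and 52% if controls do not change on average; 49%, 50% and 50% if controls gain one point.

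**Counter-case.** Assume 30% versus 65% of patients respond, responders gain 1 point plus an exponential amount with mean 6, and the rest do not change. Simulated t-test power is about 46%; exact chi-square power is about 80%.

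**Recall on the pediatric form.** With a 7-day window, 7 − 2 = 5 of the days precede injection at the day 2 call, and 7 − 6 = 1 at the day 6 call. The adult form has no such window.

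**The case against.** The strongest reply is that the plan is coherent if read generously. The one-point rule covers both appendices, so each patient could be classed as improved, unchanged or declined on their own form, the categories pooled, and chi-square applied. That also avoids averaging two different scores. This reading is open. A reader might infer that the plan has no common rule for the two forms, and the reference to both appendices contradicts that. What still stands is that the link to the test and the unit are missing. Reference 20 may supply a unit, but the plan states none for these forms.

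A reader might also infer that a chi-square test here is invalid, or that it always has less power. Neither is supported. A prespecified responder comparison is sound, and the counter-case above favours it. The size of the loss rests on an effect borrowed from pain at the least favourable correlation in Table 1. At correlation 0.3 (effect 1/1.183 = 0.845) the comparison is about 90% versus 74%, and at 0.5 (effect 1.0) it is 97% versus 87%.

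Blinding also limits the risk of a convenient choice: "Subject treatment assignments will remain blinded until the final subject has completed follow up and all data has been recorded and validated". It does not require the definition to be fixed before unblinding.

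Finally, differing construct and recall might suggest making the adult form the main analysis. That would take randomised minors out of it, although 7.0(a) commits to intention to treat, and it would cost power. At assumed pediatric shares of 10%, 20% or 30%, adults per arm would be 27, 24 or 21, and t-test power at 0.74 SD would be about 76%, 71% or 65%. The documents do not call for that split.

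**Conclusion.** The mismatch between test and outcome is plain in the text and does not depend on any power figure. Section 7.0(a) treats physical function as categorical, the outcome is change in a 10- or 8-item score, no categories are defined, and the one-point rule lacks a unit and a link to the test. The ambiguity in the unit is 8- to 10-fold between raw sum and item average.

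The power cost is conditional. With normally distributed change and 30 per arm, the best-cut chi-square trails the t-test by about 5 percentage points at 0.3 SD, 14 at 0.5, 17 to 18 at 0.74 and 10 at 1.0. If most patients do not change and the arms differ in the share who respond, the order can reverse. Every PROMIS effect and distribution used here is assumed.

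This should be corrected, but it is confined to a secondary outcome. A reader might infer that the trial's sample size is undermined; it is not, because that calculation concerns pain and uses a t-test.

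**What to change.** - In 7.0(a), move physical function from the chi-square list to the continuous outcomes. State that the PROMIS score at days 2, 6, 14 and 28 is analysed as a between-arm difference in means adjusted for its baseline value, with a 95% CI. The adjustment must be written out, because the continuous list now provides only a t-test. With equal SDs and correlation ρ, adjustment multiplies the SD of the comparison by √((1 + ρ)/2): 0.74 at ρ = 0.1, 0.87 at 0.5 and 0.97 at 0.9. This gain is not in the power figures above.
- In 2.0(c), state the score metric for each form, and so what one point means.
- Report adult and pediatric results by form, keeping all randomised patients in the analysis, for example by including form in the model on a stated common metric.
- Keep the improved, unchanged and declined proportions, defined on the stated metric and pooled across forms, as a supportive chi-square analysis. This covers the responder-type pattern.

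The cost is wording in two sections and a little extra scoring and analysis. No new data are needed: the study calendar in 5.0(f) already has PROMIS at enrollment and all four follow-ups. The wording should be settled before unblinding.

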#### Inclusion Criteria

- Age > 13 years old.
- Subject must voluntarily sign and date an informed consent, approved by an independent ethics committee / institutional review board.
- Subject is willing to comply with the procedures in this protocol.
- The subject must be diagnosed with HS and receiving care at HSC
- Subjects with Hidradenitis Suppurativa Physician Global Assessment (HS-PGA) score between 2 and 5 (Appendix A).
- The subject must have an inflamed nodule or abscess at the time of enrollment.

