### 3.0 STUDY POPULATION

- a) Study Population: The study population includes patients >13 years old with HS by a physician. All patients with HS-PGA greater than 2 will be included, regardless of comorbidities.
- b) Sample Size/Power Calculation: The primary outcome of our trial is a reduction in pain measures before and after treatment. We will have 4 groups: normal saline, ILTAC-10, ILTAC-20, and ILTAC-40. Of importance, these ILTAC doses are currently used for HS flares and are standard treatment for other dermatologic conditions, such as keloids. To estimate the sample size needed in each arm, we assumed that the pain score in our patients is normally distributed. The mean difference in pain score between normal saline and ILTAC-10 is estimated to be 1, with a standard deviation of 1, at baseline and also two days later, as is consistent with our clinical experience. We also assumed a range of correlations (0.1-0.9) that may be observed for a patient's pain score at the multiple follow-up points. When comparing normal saline and ILTAC-10, the most conservative of the treatment arms in terms of pain change, it is shown that at least 30 participants per arm are required to detect the anticipated effects (see Table 1 below for power calculations). Additionally, given that we expect to see a greater reduction in pain with ILTAC-20 and ILTAC-40, we will be more than sufficiently powered to detect the large pain reductions anticipated in the ILTAC-20 and ILTAC-40 groups. This conservative approach allows for the detection of a clinically meaningful change, as any substantial reduction in pain would result in clinical utilization of ILTAC.

**Table 1.** Tests for Two Groups of Pre-Post Scores. Numeric Results for Comparing Mean Change in a Repeated Measures Design. Null Hypothesis:  $\delta = 0$ . Alternative Hypothesis:  $\delta \neq 0$ . Results assuming a t-test.

| Target Power | Actual Power | N1 | N2 | N  | $\delta$ | $\sigma(T1)$ | $\sigma(T2)$ | $\rho$ | $\sigma(Diff)$ | Alpha |
|--------------|--------------|----|----|----|----------|--------------|--------------|--------|----------------|-------|
| 0.8          | 0.81021      | 30 | 30 | 60 | 1        | 1            | 1            | 0.1    | 1.342          | 0.05  |
| 0.8          | 0.81347      | 27 | 27 | 54 | 1        | 1            | 1            | 0.2    | 1.265          | 0.05  |

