| 0.8          | 0.8004       | 23 | 23 | 46 | 1        | 1            | 1            | 0.3    | 1.183          | 0.05  |
| 0.8          | 0.80321      | 20 | 20 | 40 | 1        | 1            | 1            | 0.4    | 1.095          | 0.05  |
| 0.8          | 0.80704      | 17 | 17 | 34 | 1        | 1            | 1            | 0.5    | 1              | 0.05  |
| 0.8          | 0.81254      | 14 | 14 | 28 | 1        | 1            | 1            | 0.6    | 0.894          | 0.05  |
| 0.8          | 0.82111      | 11 | 11 | 22 | 1        | 1            | 1            | 0.7    | 0.775          | 0.05  |
| 0.8          | 0.83633      | 8  | 8  | 16 | 1        | 1            | 1            | 0.8    | 0.632          | 0.05  |
| 0.8          | 0.87068      | 5  | 5  | 10 | 1        | 1            | 1            | 0.9    | 0.447          | 0.05  |

- Report Definitions
  - i. Target Power is the desired power value (or values) entered in the procedure. Power is the probability of rejecting a false null hypothesis. Actual power is the power obtained in this scenario. Because N1 and N2 are discrete, this value is often (slightly) larger than the target power. N1 and N2 are the number of items sampled from each population. N is the total sample size,  $N1 + N2$ .  $\delta$  is mean change of group 2 minus the mean change of group 1 assuming the alternative hypothesis.  $\sigma(T1)$  and  $\sigma(T2)$  are the standard deviations of measurements at time 1 and time 2, respectively.  $\rho$  is correlation between a pair of observations made on the same subject.  $\sigma(Diff)$  is the standard deviation of the paired differences, assumed equal for the two groups. Alpha is the probability of rejecting a true null hypothesis.
- Summary Statements
  - i. A 2-by-2 repeated measures design consists of two groups of subjects, each measured at two time points. In this case, the primary goal of the study is to compare the change across time in group 1 to the change across time in group 2. Sample sizes of 30 in group 1 and 30 in group 2 achieve 81% power to detect a difference in mean changes of 1.0 with a standard deviation of 1.0 at the first time point, a standard deviation of 1.0 at the second time point, and a correlation between measurement pairs of 0.100. The significance level (alpha) is 0.050 using a two-sided, two-sample t-test.
- c) Inclusion Criteria
  - Age > 13 years old.

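### Suppuration is a change-from-baseline outcome, but section 7.0 a) names only a chi-square for drainage and gives no role to drainage at enrolment; stratifying on it is a free gain in precision

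*Combined protocol and SAP*

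**What the plan says.** - **Outcome.** Section 2.0 a), Secondary Outcomes: "Change from baseline in subjective markers of inflammation (erythema, edema, and suppuration) at week 2 and 4".
- **Scale.** Section 2.0 c), Aim 1: "Suppuration will be measured on a dichotomous scale, by the presence or absence of purulent drainage from the lesion". The same paragraph says that changes from baseline will be compared among the treatment groups.
- **Test.** Section 7.0 a): "Categorical variables, including presence of side effects, drainage, and physical function, will be analyzed with chi square tests". The section adds "All statistical tests will be 2-sided", at the 0.05 level. It gives no visit, no arm contrast, no change category and no baseline term for drainage.
- **Who can enter.** Inclusion Criteria (sections 2.0 and 3.0 c): "The subject must have an inflamed nodule or abscess at the time of enrollment". Drainage is not required.
- **What is recorded at baseline.** Section 2.0 b), Visit 1, has the initial and all later visits document "clinical markers of inflammation, and lesion size". Purulent drainage is one of the clinical signs that Aim 1 lists.
- **Size.** Section 3.0 b): "at least 30 participants per arm are required to detect the anticipated effects". That figure is for pain. No power is stated for suppuration.

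**The concern.** For a yes/no sign, change from baseline depends on where the patient started. A patient who drains at enrolment can resolve or persist. A patient who is dry can stay dry or start to drain. If the chi-square is run on drainage at follow-up, it pools persistent drainage, new drainage and patients who never drained. Patients with nothing to resolve then dilute any drying effect, and a chance difference between arms in drainage at enrolment adds noise to the comparison.

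The wording also leaves several tables open: drainage at follow-up by arm, resolved or not by arm, or before against after within an arm. The last would treat paired values as independent and would not compare arms. At stake are the precision and readability of one secondary outcome.

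**Working it through.** **1. The plan's own figure.** The only power figure is for pain. With SD 1 at both times and correlation 0.1, SD of change = √(1 + 1 − 2 × 0.1) = 1.342. With 30 per arm and a difference of 1, the noncentrality is 1 / (1.342 × √(2/30)) = 2.89 on 58 degrees of freedom. Two-sided power at 0.05 is 0.81021, as in Table 1. I therefore take n = 30 per arm and two-sided 0.05.

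**2. Assumed inputs.** The documents give no drainage rates. I assume, with one yes/no value per patient:
- b: proportion draining at enrolment;
- persistence: proportion of these still draining at follow-up (saline/triamcinolone);
- new: proportion of patients dry at enrolment who drain at follow-up (saline/triamcinolone).

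The follow-up rate in an arm is b × persistence + (1 − b) × new.

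**3. Tests compared by simulation (40,000 to 300,000 trials per scenario).**
- Plain: uncorrected chi-square on follow-up drainage by arm.
- Stratified: Cochran-Mantel-Haenszel, [Σ(aᵢ − n_Tᵢ mᵢ/Nᵢ)]² / Σ[n_Tᵢ n_Cᵢ mᵢ(Nᵢ − mᵢ) / (Nᵢ²(Nᵢ − 1))], summed over the two strata, draining and dry at enrolment. In each stratum, a is the number of treated patients draining at follow-up, m the number draining in both arms, n_T and n_C the arm sizes, and N their sum.

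**4. One case by hand.** Take b = 50%, persistence 70/35% and new 5/5%. The follow-up rates are 0.5 × 0.70 + 0.5 × 0.05 = 0.375 on saline and 0.5 × 0.35 + 0.5 × 0.05 = 0.200 on triamcinolone. The pooled rate is 0.2875.
- Null SE = √(2 × 0.2875 × 0.7125 / 30) = 0.1169.
- Alternative SE = √((0.375 × 0.625 + 0.200 × 0.800) / 30) = 0.1147.
- z = (0.175 − 1.96 × 0.1169) / 0.1147 = −0.47, so power is about 32%. The simulation gives 31.9%.

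**5. Results.** φ is the correlation between baseline and follow-up drainage in the saline arm: b(1 − b)(persistence − new) / √[b(1 − b) p(1 − p)], where p is the saline follow-up rate.

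| Draining at enrolment | Persistence | New | φ | Plain | Stratified | Gain (points) |
|---|---|---|---|---|---|---|
| 50% | 80/40% | 0/0% | 0.82 | 39.4% | 61.5% | 22 |
| 50% | 80/40% | 5/5% | 0.76 | 37.4% | 53.7% | 16 |
| 50% | 80/40% | 10/5% | 0.70 | 45.0% | 61.0% | 16 |
| 70% | 80/40% | 5/5% | 0.70 | 60.2% | 73.6% | 13 |
| 50% | 70/35% | 5/5% | 0.67 | 31.9% | 41.9% | 10 |
| 30% | 70/35% | 5/5% | 0.69 | 17.2% | 23.1% | 6 |
| 50% | 70/35% | 20/10% | 0.50 | 45.1% | 52.5% | 7 |
| 90% | 80/40% | 10/5% | 0.47 | 83.2% | 86.9% | 4 |
| 30% | 60/30% | 10/10% | 0.53 | 13.5% | 15.2% | 2 |
| 50% | 60/30% | 40/20% | 0.20 | 51.6% | 52.6% | 1 |
| 50% | 50/20% | 50/20% | 0 | 69.0% | 68.5% | −0.5 |
| 100% | 80/40% | – | – | 90.6% | 90.6% | 0 |

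**6. No treatment effect.** The plain test rejects in 4.8 to 5.2% of trials and the stratified test in 4.5 to 5.0%.

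**7. Testing the change score (−1, 0, +1) instead.** With half draining at enrolment, a t-test on the change has power 49% against 45% for the plain test at φ 0.70, 38% against 45% at φ 0.50, and 33% against 52% at φ 0.20. The gain in step 5 therefore comes from adjusting for baseline, not from testing change as such.

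**The case against.** **The plan does not say that only follow-up status is tested.** This stands. Section 7.0 a) is silent, and a chi-square on resolved, unchanged or new by arm would fit its wording and the Aim 1 text. The word for presence may attach to side effects alone. Drainage could also mean the five-category survey item in Appendix D, and the same section assigns markers of inflammation to the t-test. The fault is under-specification, which still has to be settled before the data are seen.

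**The plain test is valid.** This stands. A reader might infer inflated type I error, because among null trials where the arms differ by 5 or more of 30 in baseline drainage (20 to 25% of trials at 30 to 70% draining, persistence 70%, new 5%), the plain test rejects 14 to 16% of the time, against about 5% for the stratified test. That figure holds only for the imbalanced trials. With 5% overall, the others must run at about (0.05 − 0.25 × 0.16) / 0.75 = 1.3% to (0.05 − 0.20 × 0.14) / 0.80 = 2.8%. Any unadjusted test behaves this way when baseline predicts outcome.

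**The size rests on chosen rates.** This also stands. The larger gains need baseline drainage to predict follow-up strongly.

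**Little depends on it.** Suppuration is one of three signs in one of many secondary outcomes, with no power claim. That sets the severity low. It does not remove the mismatch between listed outcome and stated analysis.

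**Conclusion.** The point holds as a low-severity, no-cost improvement. The outcome is a change from baseline, the only named analysis gives drainage at enrolment no stated role, and that status varies by design and is documented at Visit 1.

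Over the assumed rates, with 30 per arm, stratifying adds 0 to about 22 points of power: 6 to 22 where φ is about 0.67 or more, 2 to 7 where it is near 0.5, and essentially nothing at 0.2 or below or when all patients drain. The largest loss seen was 0.5 point.

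Three stronger readings are not supported. The documents do not show that the wrong test was chosen, since the wording is open. Randomisation protects the overall error rate of the plain test. And power is not lost because change goes untested, since a change-score test is often weaker. The primary outcome and 30 per arm are untouched.

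**What to change.** In section 7.0 a), replace the chi-square for purulent drainage with text to this effect:

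- Patient-level drainage at weeks 2 and 4 is compared between each triamcinolone arm and saline by a Cochran-Mantel-Haenszel test stratified by drainage at enrolment, or by logistic regression with drainage at enrolment as a covariate. Name one of the two as the planned analysis.
- Because drainage is defined per lesion and up to three areas may be treated, state how it becomes one value per patient. One option is any treated lesion draining, applied in the same way at baseline and follow-up.
- Report by arm the proportion resolved among patients draining at enrolment and the proportion with new drainage among patients dry at enrolment. Both are descriptive and give the reading as change.
- State that drainage here is the assessor's finding and not the survey item in Appendix D.

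The cost is a few sentences before unblinding, with no new data, visits or staff. The stratified test can be very slightly conservative when strata are sparse.
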